4.5. Information about ECG recorder

The study will use the same properly calibrated 12-channel ECG recorder CONTEC8000G ECG Workstation manufactured by CONTEC™ (China).

4.6. Estimated duration of participation of subjects, description of the sequence and duration of all stages of the study

The duration of the study for each volunteer is 2 (+7) days.

4.7. Description of conditions for termination or interruption of the entire study, its parts, or the participation of individual subjects

The study may be terminated in the event of severe adverse reactions, as well as inability to comply with the requirements of the Protocol or upon the decision of the study Sponsor. The investigator is required to inform the study Sponsor and the Ethics Committee at the HCF in writing about termination of the study.

For each volunteer, the reason for withdrawal from the study is the onset of one of the following **exclusion criteria**:

- Emergence of any medical condition, an adverse event or circumstances when, in the opinion of the investigator, it is not in the best interests of the volunteer to proceed with the participation;
- Failure to comply with the protocol requirements;
- Onset of one of the non-inclusion criteria.

The reasons for the early withdrawal of the volunteer from the study are specified in the CRF.

4.8. Accounting procedures for virtual reality headsets and volunteers

Storage of virtual reality headsets

Virtual reality headsets should be stored in original packaging, in a safe, dry place, in a closed room or a closet, accessed only by the responsible Investigator and authorized persons.

Terms of distribution, accounting and return of virtual reality headsets

For the purposes of the study, the HCF will receive 2BoboVR X1 virtual reality headsets with pre-installed software (sham and Pure Purr). Each virtual reality headset will be labelled as A or B.

Having received the virtual reality headsets, the responsible Investigator provides signing of the Note of Delivery to the Study Site (2 copies) by the administration of the HCF. All received virtual reality headsets should be registered on the off-balance sheet of the HCF.

Under no circumstances can the investigator allow the use of virtual reality headsets for any purposes other than that specified in the Clinical Study Protocol. The virtual reality headsets should be delivered to the SS in intact packaging.

Upon completion of the study the virtual reality headsets are returned to the Sponsor, as evidenced by the Note of Return from the Study Site (2 copies).

The Investigator conducting the study should keep the Virtual Reality Headset Use Form, stating the following

- 1) Date, time and duration of use of the virtual reality headset
- 2) Type of headset, A or B
- 3) Volunteer's ID

The virtual reality headset will be used by the volunteers in accordance with the regimen corresponding to the study group

Record form for enrolled/screened/randomized volunteers

Volunteers who have signed the Informed Consent Form are registered in the Record Form for Enrolled/Screened/Randomized Volunteers, which states:

- 1) Volunteer's full name
- 2) Volunteer's ID (five digits)
- 3) Date of signing of the Informed Consent Form
- 4) Did the volunteer pass the screening (yes/no)?

- 5) Did the volunteer pass the randomization (yes/no)?
- 6) Date of randomization
- 7) The group to which the volunteer was assigned (1 or 2)
- 8) In case of volunteer's non-compliance based on the results of the screening or his/her exclusion, the reason should be specified in the Volunteer Exclusion column

4.9. Disclosure of randomization code

Information related to decoding of randomization codes will be retained by the Sponsor throughout the study. Disclosure of randomization codes will be carried out after the Sponsor receives statistical data on the findings and outcomes of the study.

An Authorized Representative of the Sponsor retains confidentiality of randomization codes and cannot disclose them directly or indirectly to volunteers or other parties/individuals/entities.

4.10. Working with Case Report Forms

All data entered in the Case Report Forms are considered to be source documentation.

Data on each volunteer enrolled in the study should be collected by the Investigator 2 times (Visit 1 and 2). Only the person to whom this right has been delegated in accordance with the Distribution of Duties and Signature Samples Log is allowed to make entries and corrections in the CRF.

4.11. Description of the sequence and duration of the stages of the CS before the use of the virtual reality technology

In order to enrol a volunteer in the study, the investigator has to take a number of consecutive steps:

1. Fill in and sign the Informed Consent Form with the volunteer. The terms and conditions of the study should be explained to potential study subjects and suggested to familiarize themselves with the Study Subject Information Sheet. A potential study participant should have enough time to familiarize himself/herself with the information, he/she has the right to ask any study-related questions, he/she should receive comprehensive information regarding his/her inquiries. Participation in the study is absolutely voluntary. In case of consent to participate in the study, the volunteer gives his/her written consent to participate in the study by signing the Informed Consent Form. 2 copies of the Informed Consent Form should be signed and dated by the participant in person, as well as the person, who informed study subject (the investigator).

2. The investigator should check the volunteer's compliance with the eligibility criteria for inclusion/non-inclusion. For the purposes of testing, the investigator adds the information about verification of the availability of all inclusion criteria and the absence of all non-inclusion criteria to the CRF.

3. Randomization will be carried out only after the signing of the Informed Consent Form and verification of the volunteers' compliance with all inclusion/non-inclusion criteria.

4. Once the volunteer has been successfully randomized, the investigator should indicate the volunteer's (five-digit) identification number:

- in the CRF;
- in the Virtual Reality Headset Use Form;
- in the Record Form for Enrolled/Screened/Randomized Volunteers.

4.12. Time and events schedule

The frequency of examination in volunteers and registration of the data obtained will be carried out in accordance with the schedule shown in Table 4.

Table 3. Visit matrix (time and events schedule)

Study procedures		
Visits ¹	Visit 1	Visit 2
Study days	Day 1	Day 2 (+7)
Basic data		

Study procedures		
Visits ¹	Visit 1	Visit 2
Study days	Day 1	Day 2 (+7)
Obtaining informed consent	X	
Evaluation of volunteer's compliance with the inclusion/non-inclusion criteria	X	
Randomization	X	
Evaluation of availability of exclusion criteria		X
Registration of demographic data	X	
Collection of medical history	X	
Physical examination	X	X
Measuring BP, HR, RR, and body t°	X	X
Registration of concomitant treatment and comorbidities	X	
Investigation of the VR technology		
Stress modulation and EGC recording before/during/after VR exposure	X	X
Evaluation of volunteers based on the Spielberger State-Trait Anxiety Inventory (STAI)	X	X
Safety and tolerability evaluation		
Registration of AR/ADE	X	X
Tolerability evaluation	X	X

4.13. Study procedures and methods used throughout the study

Obtaining informed consent

All volunteers must provide the written informed consent to participate in the study before study initiation.

Volunteers, who are potential participants in the study, should be informed by the investigator in a clear form about the nature of the clinical trial, the technology under investigations, and the possible risks associated with administration of the medicinal product. All information and the Informed Consent Form are given to the volunteers at their request in Russian or in Ukrainian.

The volunteers should be informed that at any given moment they may refuse to participate in the study. The volunteers should know that the fact of their participation in the study is strictly confidential.

The volunteers also have to be explained that their personal data obtained during the study will be used for statistical processing of the study results and drawing of a report, and can also be discussed by the individuals conducting the study.

A volunteer should be given enough time to make a decision regarding participation in the study and have the opportunity to discuss all questions with his or her investigator. The investigator should not put pressure on the volunteer to have an effect on his/her decision.

2 copies of the Informed Consent Form should be signed and dated by the volunteer in person, as well as the person, who informed the volunteer (the investigator). One copy of the signed and dated Informed Consent Form is given to the volunteer, the second copy will be attached to the Investigator's File and the SS archive for at least 15 years upon the completion of the trial.

In the event that new safety data are obtained that will lead to a significant change in the risk/benefit ratio, it is necessary to analyse the Informed Consent Form and introduce the necessary changes. In this case, the volunteers, who continue to participate in the study, should be informed of the emergence of new information, provide them with a new version of the Informed Consent Form, and give them the opportunity to reconsider their decision to participate in this study, to sign and to date 2 copies of the Informed Consent Form for participation in the clinical trial.

The fact of obtaining informed consent must be recorded in the CRF with indication of the date of signing the Informed Consent Form.

Screening procedures/evaluation for collection of data on the volunteers' baseline condition/volunteers' inclusion to the study

Upon obtaining of the informed consent, it is necessary to confirm the possibility of the volunteer's participation in the study based on the inclusion/non-inclusion criteria. For this purpose, it is necessary to conduct an examination, which includes:

- registration of demographic data (sex, age) and anthropometric data (height, body weight, BMI calculation);
- objective examination;
- measurement of BP, HR, and body t°;
- collection of medical history;
- data on current treatment;
- evaluation of volunteer's compliance with the inclusion/non-inclusion criteria.

Confirmation of compliance with each of the inclusion/non-inclusion criteria should be reflected in the relevant sections of the CRF.

Simulation of stress using calculations in head

During each visit, prior to the investigation of the effects of the audio-visual sequence in the VR, volunteers will undergo a 5-minute mental calculation test. The investigator or his assistant will read for the volunteers two three-digit numbers, which the volunteers have to add and state their sum, which they will have to decompose and sum up to obtain a one-digit number. In the case the volunteer gives a wrong answer, the investigator clearly tells him/her about it and says "that is not correct". Volunteers will hear the same sets of three-digit numbers.

Measurement of BP and HR

Measurement of HR and BP will be performed with the help of properly calibrated equipment at the study site in a sitting position after at least a 5-minute rest.

Measurement of body temperature

Measurement of body temperature will be done for 10 minutes in the armpit using a mercury thermometer once during each visit.

Physical examination

It includes: auscultation of the heart and lungs, examination of skin, organ systems, and visible mucous membranes. Objective examination is carried out during each visit in full.

Anthropometric data

Collection of anthropometric data (height and weight) will be carried out using equipment available at study sites during visits to the SS at visit 1.

Electrocardiography

Electrocardiograms will be taken by the properly qualified investigator, the study will use the same properly calibrated 12-channel ECG recorder CONTEC8000G ECG Workstation manufactured by CONTEC™ (China).

Spielberger State-Trait Anxiety Inventory

Testing the volunteers using the Spielberger STAI will be performed in the process of assessment of compliance with the inclusion/non-inclusion criteria, and upon completion of investigation of the virtual reality technology.

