4.3. Description of randomization and blinding

In order to observe the “blindness”, the study group of each volunteer will be determined in accordance with their randomization group.

The blind study suggests volunteers’ lack of information about used VR technology. VR headsets will be labelled as A and B, and the volunteer will not be aware of the corresponding technology. Unblinding will take place upon completion of the study.

With a view to a more even distribution of the volunteers, a block randomization design (fixed-length blocks of 10 volunteers balanced by groups) will be used.

Randomization is carried out only after the signing of the Informed Consent Forms and verification of the volunteers’ compliance with all inclusion/non-inclusion criteria (the volunteers are assigned with randomization numbers).

In practice, the implementation of the developed randomization scheme will be carried out using numbered envelopes provided by the Sponsor to the site. Each envelope will contain 10 randomization cards. The investigator will open an envelope and randomly take out randomization cards, which will say “Group 1” or “Group 2”, according to which the volunteers will take part in the study.

The next envelope will be opened as the investigator runs out of randomization cards in the previous envelope in ascending order of the numbers on envelopes.

The distribution by groups is given in Table 2.

Table 2. Distribution of healthy volunteers

	Group 1	Group 2
Number of volunteers	50 healthy volunteers	50 healthy volunteers

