6. STUDY SUBJECT INVESTIGATION

6.1. Procedure for use of the virtual reality technology

Depending on the results of randomization, the volunteers are assigned to Group 1 or Group 2:

Group 1: the volunteers will first be tested with the VR headset A, and during the next visit – with the VR headset B.

Group 2: the volunteers will first be tested with the VR headset B, and during the next visit – with the VR headset A.

Stages for each visit

Volunteers' tests during each visit consist of the following stages:

Stage 1, a volunteer lies down on the bed and 5-minute ECG is recorded at rest.

Stage 2, a volunteer undergoes the software-based "mental calculation" test while lying on the bed for 5 minutes. ECG is recorded simultaneously.

Stage 3, a volunteer lies down on the bed, puts on the VR headset, the investigator turns the program on for 5-minute exposure, ECG is recorded simultaneously.

Stage 4, a volunteer takes off the VR headset, lays on the bed for 5 minutes during which ECG is recorded, then the volunteer takes the Spielberger State-Trait Anxiety Inventory (STAI).

Thus, for each visit, 4 ECG will be registered for each volunteer: before the test, during the test, and after the test. Two assessments based on the Spielberger State-Trait Anxiety Inventory (STAI) will be carried out, as well: before the use of the virtual reality technology and after the use of the virtual reality technology.

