Attachment No. 2. Numeric character sets for mental calculation

Volunteer's ID: _____

- 1) 854 + 746 = 1600 =7
- 2) 191 + 733 = 924 =14 =5
- 3) 793 + 966 = 1759 =23 =5
- 4) 555 + 419 = 974 =20 =2
- 5) 271 + 955 = 1226 =11 =2
- 6) 591 + 862 = 1453 =13 =4
- 7) 688 + 531 = 1219 =13 =4
- 8) 358 + 696 = 1054 =10 =1
- 9) 422 + 685 = 1107 =9
- 10) 772 + 969 = 1741 =13 =4
- 11) 493 + 650 = 1143 =9
- 12) 128 + 822 = 950 =14 =5
- 13) 752 + 383 = 1135 =10 =1
- 14) 764 + 550 = 1314 =9
- 15) 408 + 807 = 1215 =9
- 16) 194 + 467 = 661 =13 =4
- 17) 299 + 959 = 1258 =16 =7
- 18) 502 + 325 = 827 =17 =8
- 19) 302 + 552 = 854 =17 =8
- 20) 562 + 891 = 1453 =13 =4
- 21) 339 + 930 = 1269 =18 =9
- 22) 826 + 397 = 1223 =8
- 23) 196 + 427 = 623 =11 =2
- 24) 576 + 252 = 828 =18 =9
- 25) 120 + 788 = 908 =17 =8
- 26) 323 + 735 = 1058 =14 =5
- 27) 759 + 132 = 891 =18 =9
- 28) 839 + 723 = 1562 =14 =5
- 29) 493 + 685 = 1178 =17 =8
- 30) 520 + 685 = 1205 =8
- 31) 220 + 560 = 780 =15 =6
- 32) 222 + 921 = 1143 =9
- 33) 457 + 734 = 1191 =12 =3
- 34) 549 + 528 = 1077 =15 =6
- 35) 392 + 838 = 1230 =6
- 36) 886 + 560 = 1446 =15 =6
- 37) 294 + 460 = 754 =16 =7
- 38) 805 + 382 = 1187 =17 =8
- 39) 413 + 895 = 1308 =12 =2
- 40) 151 + 461 = 612 =9
- 41) 768 + 861 = 1629 =18 =9
- 42) 516 + 272 = 788 =23 =5
- 43) 172 + 373 = 545 =14 =5
- 45) 371 + 103 = 474 =15 =6
- 46) 220 + 931 = 1151 =8
- 47) 118 + 219 = 337 =13 =4
- 48) 371 + 993 = 1364 =16 =7
- 49) 596 + 620 = 1216 =10 =1
- 50) 329 + 486 = 815 =14 =5

State the number of successful calculations: _____

Comment:

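### Stage 2 is a software-based stress test in the synopsis and 6.1 but is read aloud by staff in 4.13; in the spoken mode, someone who can know the coming headset sets the stressor

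*Protocol*

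**What the plan says.** **Mode of delivery.** For Stage 2, protocol 6.1 says that "a volunteer undergoes the software-based" mental calculation test, lying down, for five minutes with simultaneous ECG. The synopsis says the same. Section 4.13, under simulation of stress, describes something else: "The investigator or his assistant will read for the volunteers two three-digit numbers, which the volunteers have to add and state their sum". It continues: "In the case the volunteer gives a wrong answer, the investigator clearly tells him/her about it". Attachment 2 is a printed list of sums with worked answers and a line for the reader to fill in, "State the number of successful calculations", which fits the spoken mode.

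**What is fixed.** Section 4.13 fixes the five-minute duration, the phrase used after a wrong answer, and the content: "Volunteers will hear the same sets of three-digit numbers". It does not fix reading pace, tone, number of items, or having the same reader at a volunteer's two visits.

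**Who knows what.** Section 4.3 describes blinding as the volunteers' "lack of information about used VR technology". On allocation it says "The investigator will open an envelope and randomly take out randomization cards". Under 4.2, randomization comes before testing at Visit 1. Under 4.8, the investigator keeps a log that includes "Type of headset, A or B" for each volunteer. Under 6.1, the investigator starts the VR program. Section 9.1 states that headset A is the investigational device and B the comparator. Section 4.9 leaves the decoding information with the sponsor.

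**The concern.** The primary objective is autonomic recovery after this stressor, and Stage 2 comes immediately before the headset. How hard the volunteer is stressed is therefore part of the experimental condition. A site cannot tell from the protocol whether to run a program or read from a sheet.

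If a person reads, the strength of the stressor depends on pace, manner and how errors are called out. The investigator, who gives the feedback under 4.13, already knows which letter follows, and a reader of 9.1 also knows what A means. Nobody need intend anything for the stress to differ slightly before A and before B. A difference of that kind would appear as a headset effect in the primary variable, and it could not be repaired after the data are collected.

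**Working it through.** **1. The texts side by side.**

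| Place | Delivery of Stage 2 |
|---|---|
| Synopsis, 6.1 | Software-based test |
| 4.13 | Investigator or assistant reads; investigator announces errors |
| Attachment 2 | Paper list with answer key and handwritten count |

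Software might only supply or time items that a person then reads, which would reconcile these texts, but no section says so.

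The paper key also has errors that matter if a person reads from it. Repeated digit sums of 924, 1759, 1308 and 1364 are 15→6, 22→4, 12→3 and 14→5. Items 2, 3, 39 and 48 print final digits 5, 5, 2 and 7. A reader following the sheet would reject correct answers. The sheet is the same at both visits, so this alone does not favour a headset.

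**2. Can the analysis remove a stress difference?** The model in 9.2.3 has sequence, period, headset, and subject within sequence. Let τ be the true A-B difference, π the period difference (period 1 minus period 2), and b a shift in the outcome whenever A follows, caused by uneven stress.

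- Group 1 (A then B): expected period 1 minus period 2 = τ + b + π
- Group 2 (B then A): expected period 1 minus period 2 = −τ − b + π
- Half the difference between groups = τ + b

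The period effect cancels. The shift b does not, at any sample size.

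**3. Size of b, illustration only.** Section 9.2.3 analyses X(%) = 100 × (after − before)/before but does not say which stage is before. The HF shifts below are assumptions; the protocol gives none.

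*Stage 2 as baseline.* Let R be the after/before HF ratio under B, with no true headset effect, Stage 4 unaffected, and Stage 2 HF lower by a fraction c before A. Then b = 100 × R × [1/(1 − c) − 1]. With R = 1.0:

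| c | b (percentage points) |
|---|---|
| 0.05 | 1/0.95 − 1 → 5.3 |
| 0.10 | 1/0.90 − 1 → 11.1 |
| 0.15 | 1/0.85 − 1 → 17.6 |

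For comparison, 9.1 uses a superiority limit of 0.10 and an assumed difference of 0.25. At c = 0.10, R from 0.8 to 1.5 gives 8.9 to 16.7 points. If the stronger stress also lowers Stage 4 by a fraction q, the term becomes (1 − q)/(1 − c) − 1, which shrinks to zero when q = c.

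*Stage 1 as baseline.* X(%) then contains no Stage 2 value. With Stage 4 unaffected, b = 0. If stress carries over and lowers Stage 4 by q, b = −100 × R × q, which works against A.

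**4. Noise rather than bias.** The plan's own figure reproduces: n = (1.96 + 1.64)² × 0.35² / (2 × (0.25 − 0.10)²) = 12.96 × 0.1225 / 0.045 = 35.28, rounded up to 36. Suppose reader changes add an SD of 0.10 to 0.20 (assumed). The variance factor is (0.1225 + 0.01)/0.1225 = 1.08 to (0.1225 + 0.04)/0.1225 = 1.33, and n becomes 12.96 × 0.1325/0.045 = 38.2, so 39, to 12.96 × 0.1625/0.045 = 46.8, so 47. About 100 volunteers are to be randomized.

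**The case against.** The case on the other side has real force.

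- **Standardisation exists.** Content, duration and feedback phrase are fixed, the count of correct answers gives a check at each visit, there is one centre, and section 11 provides staff training at initiation. Pace and tone often sit in a training manual. This narrows what can vary, but it does not settle which mode is used or who delivers it.
- **The investigator may know only a letter.** Section 4.9 and the telephone unblinding route in section 8 suggest that the treatment behind the letter was meant to stay hidden from the site. That intention is undone by 9.1, which prints what A is.
- **Stage 2 may not be the baseline.** The synopsis labels the four ECGs in an order that makes Stage 1 the recording before VR exposure. On that reading the 5 to 18 points disappear unless stress carries over. This stands, and it is why no single figure can be given.

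Three stronger readings are tempting and not supported. One is that whoever reads the sums knows the headset: the protocol does not say what the assistant knows. Another is that a Stage 1 baseline simply reverses the bias: with Stage 4 unaffected it gives none. The third is that uneven reading threatens power: the added noise is largely absorbed by about 100 randomized against 36 required.

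**Conclusion.** The contradiction between the synopsis and 6.1 on one side and 4.13 with Attachment 2 on the other is on the face of the text and must be reconciled. If the spoken mode is used, the protocol allows the stressor to be shaped by a person who can know which treatment follows, and the planned model cannot separate a resulting stress difference from the headset effect on HF. With a fully automated test, this route largely closes.

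The protocol shows a route for bias, not that bias will occur. The size is unknown. The range of 5 to 18 percentage points rests on hypothetical HF shifts of 5% to 15%, a Stage 2 baseline, an after/before ratio of 1.0 and no carry-over into Stage 4. The sample size of 36 is unaffected.

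**What to change.** Settle on one mode and make the synopsis, 4.13, 6.1 and Attachment 2 agree. The preferable choice is to present the numbers by software or recorded audio at a fixed pace, identical at both visits, with scripted feedback on errors. Correct the four wrong answers in Attachment 2 in either case.

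If a person must read or give feedback, require the same person at both visits of a volunteer, working to a timer and unaware of the group and of the headset that follows. That rules out the investigator who drew the card, so the option of an assistant should stay in that case, and the error feedback should pass to that person too. State in 4.3 who is kept unaware.

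The cost is a wording change plus one recording or simple program, which the synopsis and 6.1 already presuppose. In the spoken mode it is a division of tasks between existing staff. The change has to be made before enrolment.

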4.14. Study data collection procedure

The study will be collected according to the following plan:

Visit 1.

The visit takes place at the SS and is considered to be Day 1 of the study.

Having received the informed consent for participation in the study, the investigator evaluates the compliance of the volunteer with the inclusion criteria and verifies that he/she has no non-inclusion criteria.

During the visit, the investigator:

- Obtains the Informed Consent Form from the volunteers;
- Checks the inclusion/non-inclusion criteria, evaluates the volunteers with the help the Spielberger STAI. In case a volunteer has all the inclusion criteria and no signs that meet the non-inclusion criteria, the investigator performs further data collection and randomization;
 - Anthropometric data (weight, height and body mass index);
 - Evaluates vital signs (BP, HR, RR, and body t°);
 - Physical examination;
 - Collects demographic data (date of birth, gender);
 - Collects clinical data on concomitant diseases, therapy and records them;
 - Investigates the technology of virtual reality (Stages 1, 2, 3, and 4);
 - Evaluates the volunteers' complaints in terms of the development of adverse events/adverse device effect (AE/ADE);
 - Evaluates tolerability;
 - The clinician records all indicators collected at Visit 1 and transfers them to the CRF.

Visit 2.

The visit takes place at the SS.

During the visit, the Investigator:

- Checks the inclusion criteria. In case a volunteer has no signs that meet the exclusion criteria, the Investigator performs further data collection;
 - Evaluates vital signs (BP, HR, RR, and body t°);
 - Evaluated physical signs;
 - Investigates the technology of virtual reality (Stages 1, 2, 3, and 4);
 - Evaluates volunteers based on the Spielberger State-Trait Anxiety Inventory (STAI);
 - The investigator records all indicators collected at Visit 2 and transfers them to the CRF;
 - Evaluates the volunteers' complaints in terms of the development of adverse events/adverse device effect (AE/ADE);
 - Evaluates tolerability;
 - Informs volunteers on study completion.

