7. EFFICACY EVALUATION

7.1. Efficacy parameters

Principal and secondary parameters to be determined during the study:

Primary variable:

- Change in HF component after 5-minute exposure to the VR audio-visual sequence;

Secondary variables:

- Change in rMSSD after 5-minute exposure to the VR audio-visual sequence;
- Change in LF/HF ratio after 5-minute exposure to the VR audio-visual sequence;
- Change in SDNN after 5-minute exposure to the VR audio-visual sequence;
- Change in TP after 5-minute exposure to the VR audio-visual sequence;
- Change in HR after 5-minute exposure to the VR audio-visual sequence;
- Change in BP after 5-minute exposure to the VR audio-visual sequence;
- Change in Spielberger State-Trait Anxiety Inventory (STAI) score after 5-minute exposure to the VR audio-visual sequence.

The criterion for the prevailing efficiency for each variable is the presence of statistically significant differences between groups in favour of any of the groups with a directivity, which indicates the effectiveness of the technology. Procedures and methods required for efficacy evaluation are described in Section 4.13. The time and events schedule is shown in Section 4.12.

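### The protocol contradicts itself on whether a pre-headset STAI is taken at Visit 2, so the baseline for the second headset's change score is not fixed

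*Protocol*

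**What the plan says.** - **Section 4.13** gives the procedure for STAI timing: testing "will be performed in the process of assessment of compliance with the inclusion/non-inclusion criteria, and upon completion of investigation of the virtual reality technology".
- **Section 4.12, Table 3** marks "Evaluation of volunteer's compliance with the inclusion/non-inclusion criteria" at Visit 1 only and "Evaluation of availability of exclusion criteria" at Visit 2 only. The STAI row is marked at both visits, without a number of administrations or a time within the visit.
- **Section 4.14** has at Visit 1: "Checks the inclusion/non-inclusion criteria, evaluates the volunteers with the help the Spielberger STAI". At Visit 2 it has one separate STAI entry, listed after the entry for Stages 1 to 4. The first Visit 2 entry mentions a check of inclusion criteria, then turns to exclusion criteria, and does not name the STAI.
- **Section 6.1** puts one STAI in the stage descriptions, at the end of Stage 4. Its closing paragraph begins with a per-visit count of ECGs and goes on to say that there will be two STAI assessments: "before the use of the virtual reality technology and after the use of the virtual reality technology".
- **Section 7.1** lists the secondary endpoint as "Change in Spielberger State-Trait Anxiety Inventory (STAI) score after 5-minute exposure to the VR audio-visual sequence". **Section 9.2.3** has each quantitative variable analysed as a percentage change from before to after the headset's exposure. **Section 4.1** and the synopsis word the STAI endpoint as a value after exposure.

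**The concern.** The endpoint in Section 7.1, analysed as in Section 9.2.3, needs a before and an after score for each headset. The two headsets are used on different days: at least 24 hours apart, with Visit 2 allowed to slip by up to 7 days. Attachment 1 asks how the volunteer feels at the time of completion, so a score from Visit 1 does not describe the volunteer's state just before the second headset.

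If a site works from 4.13 and 4.14, the second headset (B in Group 1, A in Group 2) may have no before score from its own visit. Situational anxiety is the whole of the secondary objective and the STAI is its only measure. A state score that was not taken on the day cannot be reconstructed at analysis.

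**Working it through.** **Reading the sections together**

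1. Section 4.13 ties the first STAI to the inclusion/non-inclusion check. Table 3 places that check at Visit 1 only. So 4.13 with Table 3 gives a pre-headset STAI at Visit 1 and none at Visit 2.
2. The Visit 2 check in Table 3 concerns exclusion criteria (Section 5.3). These include onset of a non-inclusion criterion, but the STAI level is an inclusion criterion (Section 5.1, item 4). The exclusion check therefore does not by itself call for a STAI.
3. Section 4.14 incorporates Stages 1 to 4 at both visits, and Stage 4 contains a STAI. The separate Visit 2 entry then either repeats the Stage 4 form or is a pre-exposure form listed out of order. The text does not say which.
4. Section 6.1 makes its STAI statement in a paragraph that opens with a per-visit count. The natural reading is two per visit, which conflicts with step 1.
5. Table 3 marks the STAI at both visits without timing, so it cannot settle the conflict.

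**Forms collected**

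The protocol states no number of forms to reproduce. Taking 100 randomized volunteers (Section 4.3, Table 2), all completing both visits:

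- Section 6.1 read per visit: 100 × 2 visits × 2 forms = 400.
- Section 4.13 with the Stage 4 form: 100 (Visit 1 before) + 100 (Visit 1 after) + 100 (Visit 2 after) = 300.
- Difference: 400 − 300 = 100, which is every Visit 2 baseline, or 100 of 200 visit-level baselines.

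**Effect on the headset contrast**

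Let b1 be the Visit 1 baseline. If it serves both headsets, the contrast in absolute change is (post_A − b1) − (post_B − b1) = post_A − post_B. The baseline cancels. In percentage form the contrast is 100 × (post_A − post_B) / b1.

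Illustration for one Group 1 volunteer, with assumed scores b1 = 36, post_A = 33, post_B = 35:

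- Shared baseline: (33 − 36) − (35 − 36) = −2, and 100 × (−2)/36 = −5.6 percentage points.
- With an own Visit 2 baseline assumed to be 40: (33 − 36) − (35 − 40) = +2, and 100 × (−3/36) − 100 × (−5/40) = −8.3 + 12.5 = +4.2 percentage points.

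The two definitions can differ in sign for the same volunteer, so they are different quantities.

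**Precision**

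Assume unit variance per score, correlation r_v between scores within a visit, and correlation r_b between any two scores from different visits.

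- Shared baseline: variance of the contrast = 2(1 − r_b).
- Own-visit baselines: variance = 4(1 − r_v), because the between-visit terms cancel.

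Over r_v = 0.5 to 0.9 and r_b = 0.3 to 0.7, with r_b no larger than r_v, the shared form gives 0.6 to 1.4 and the own-visit form 0.4 to 2.0. Neither is always more precise.

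**Sample size**

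Section 9.1 gives (1.96 + 1.64)² × 0.35² / (2 × (0.25 − 0.10)²) = 35.28, rounded up to 36, as stated. It concerns the HF endpoint and does not depend on the STAI schedule.

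**The case against.** A reader might infer that the protocol schedules no pre-headset STAI at Visit 2. The documents do not support that. The Section 6.1 statement sits under a heading and in a paragraph about each visit, and most naturally gives Visit 2 its own baseline. Table 3 marks the STAI at Visit 2. The Visit 2 list in 4.14 mentions the inclusion criteria, one of which is the STAI level. The order of entries in 4.14 is not reliably chronological either: at Visit 2, recording all indicators precedes the adverse event questions, so the position of the STAI entry proves little. It is also tempting to count only the STAI entries named separately in 4.14 and arrive at 200 forms, but that ignores the Stage 4 form incorporated at both visits.

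The consequences are also bounded. The STAI is one of seven secondary variables, and Section 4.1 and the synopsis word it as a post-exposure value, which needs no baseline. With a shared baseline the contrast is a post-score comparison that the randomized crossover supports.

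All of this stands against a claim of outright absence. It does not remove the contradiction. Neither the stage descriptions nor any Visit 2 entry in 4.14 explicitly puts a STAI before the headset, and the Visit 2 mention of inclusion criteria names no STAI and conflicts with Table 3 and Section 4.2. If 6.1 does mean two per visit, then 4.13 is wrong and needs correcting all the same.

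**Conclusion.** The protocol is internally inconsistent about the Visit 2 baseline for the STAI; the baseline is unsettled, not shown to be missing. If a site follows 4.13 and 4.14 in the narrower sense, about 300 forms are collected in place of 400, and no volunteer has an own-visit change under both headsets. The second headset's change would then use a screening score taken one to eight days earlier, before the first exposure. A reader might go further and conclude that the headset comparison on anxiety would be lost or invalid. It would not: a randomized comparison of post-exposure scores remains, though it is not the per-headset change that Sections 7.1 and 9.2.3 define.

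Severity is moderate: a secondary endpoint is affected, and the primary HF endpoint and sample size are not. The counts assume 100 volunteers with both visits completed; the scores and correlations in the illustration are assumed and serve only to show that the two definitions differ.

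**What to change.** Reconcile Sections 4.12 (Table 3), 4.13, 4.14 and 6.1 before enrolment:

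- Give the STAI before Stage 1 and at the end of Stage 4 at both visits. The Visit 1 eligibility score already falls before Stage 1 and can serve as that visit's baseline.
- Split the STAI row of Table 3 into a before-Stage-1 row and an end-of-Stage-4 row, each marked at both visits.
- In 4.14, name both administrations at each visit, in the order in which they happen.
- State that each visit's pre-Stage 1 score is the baseline for that visit's headset, and that the Visit 2 score is not an eligibility test.

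The cost is at most one extra 20-item form per volunteer at Visit 2 (none if two per visit was already intended) and wording changes in four places. The form is already in Attachment 1.
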